The primary endpoint upon which the powering analysis is performed using the vAUC from the qPCR for all collected samples, compared between groups using a Mann-Whitney U Test (Wilcoxon rank sum). The assumptions are based on the Placebo data from two prior challenge studies with this H3N2 virus. The study is powered to detect as low as a 20% efficacy of the vaccine using this endpoint at a power of 80%, and approximately 25% efficacy at a 90% power. This allows for up to 20% drop out without prejudicing the goal of the study.

Secondary endpoints include the rate of virologically confirmed ILI (symptoms of either an upper or lower respiratory illness along with two positive PCR or culture) measured between groups. Another key secondary endpoint of relevance to the biologic effect of this vaccine will be the comparison of the symptom severity as a total Area Under the Curve (AUC). This endpoint takes into account both the severity and the duration of symptoms. Mucosal secretions will be collected, and the weight of the sample tissues compared between groups.

Importantly, with a 83% attack rate and 30% efficacy, approximately 20 of the 80 vaccinated participants will have a zero AUC, and these participants can be compared to those with the highest vAUC in correlate of protection analyses.

Safety will be reported using standard frequency and severity tables.

At the protocol sample size, there is a 93% chance that a Serious Adverse Event (SAE) with a 3% incidence will be observed in at least one participant.

TIME AND EVENTS SCHEDULE

Period 1- Screening and Vaccination Schedule

Period 1	Screening 1	Screening 2	Baseline Vaccination	Out patient Clinic Visit	Phone ⁸	Out patient Clinic Visit	Out patient Clinic Visit	Phone ⁸	Unscheduled visit ⁷	See Challenge Day -2	Phone
	Days -42 to -2	Day -21 to -1	Day 1	Day 2	Day 4	Day 8 ±1 (Week 1 Visit)	Day 28 ±3	Day 56 ±3			Month 6 (180 ±14 days) ⁹
Informed Consent	x ¹	x ¹									
Inclusion/Exclusion	x ²	x ²									
Randomization			x								
Medical History/Demography		x									
Physical Examination		x ^{2a}				x	x		x		
Vital Signs		x				x	x		x		
Supine 12-lead ECG		x									
Haematology		x							x		
Biochemistry ^{2b}		x							x		
Microneutralization (MNT) ¹	x	x ¹									
Urinalysis		x							x		
HIV,, Hep C, HBsAg		x									
Urine Drug Screen		x	x						x		
Alcohol breath test		x	x						x		
Serum/Urine Pregnancy ³		x	x						x		
Blood sample for cellular immunogenicity assays PBMCs ⁴ , and Serum			x ^{4a}			x	x				

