
Prior and concomitant medications will be coded using the World Health Organization (WHO)_DRUG Dictionary.

9.1.2 *Efficacy Data*

A more detailed description of all efficacy analyses will be included in the trial's SAP, including planned supportive and sensitivity analyses, as well as methods for imputing missing data.

9.1.2.1 *PRIMARY ENDPOINT*

The trial's primary endpoint is a comparison of the viral shedding of influenza virus in MVA-NP+M1 versus placebo recipients following human challenge, as measured by the cumulative area under the curve (vAUC). Difference in vAUC, as measured and quantitated by log-transformed qPCR, will be evaluated using a Mann-Whitney U Test. AUC will be calculated using the trapezoidal rule. In case no viral load was detected, the \log_{10} viral load will be imputed.

Mean (\pm Standard Error (SE)) viral load over time will be summarized and presented graphically in \log_{10} scale by treatment group.

9.1.2.2 *SECONDARY ENDPOINTS*

The attack rate, defined as percentage of inoculated participants with at least two positive swabs as determined by qPCR, will be summarized in percentages and 95% confidence intervals (CIs) by treatment group. The difference between the two treatment groups will be compared by a Fisher's exact test.

Time to start, time to peak and time to cessation of viral shedding from virus inoculation and duration of viral shedding will be summarized by the Kaplan-Meier method. Differences between the treatment groups will also be tested using the log-rank test. Differences in peak between treatment groups will be tested using a Mann-Whitney U test.

The same analyses as performed for qPCR will be performed on quantitative culture.

Secondary endpoints include the rate of virologically confirmed ILI (defined as a respiratory or flu-like symptom occurring on two consecutive days, along with a positive PCR or culture) measured between groups. Incidence of laboratory-confirmed influenza will be compared between vaccine groups using Fisher's Exact Test.

Another key secondary endpoint of relevance to the biologic effect of this vaccine will be the comparison of the symptom severity as an AUC. This endpoint takes into account both the severity and the duration of symptoms. Total and individual symptom scores from Day 1 to Day 11 post-challenge, will be compared by AUC using a Mann-Whitney U test.

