1.2 STUDY DESIGN

This is a randomized, single-centre, double blind study. The study screens healthy volunteers and only enrolls those with microneutralisation test (MNT) < 20. The study consists of an outpatient vaccination phase, and at least 6 weeks later an inpatient challenge phase.

155 participants are randomized 3:2 to receive either MVA-NP+M1 (N=93) or Placebo (N=62) by intramuscular injection in the non-dominant arm deltoid. Vaccination-related local and systemic symptoms are followed by participant-directed diary cards for 7 days, and unsolicited adverse events are followed throughout the study from consent signature.

A total of 80 participants from the MVA-NP+M1 group and 54 from the saline Placebo group are challenged. Participants enter the quarantine facility on Day -2 or Day -1 and are discharged on Day 11. Participants receive a single intranasal administration of the H3N2 challenge agent via nasal spray. Challenge-related local and systemic symptoms are followed up to twice a day using investigator-directed symptom score cards for 11 days.

The schedule of assessments is in section 9.4.1 for the vaccination period and in section 9.4.2 for the challenge period.

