- AUC will be rounded as detailed in section 5.3.4.
- Missing values will be imputed as detailed in section 5.3.1.

2.1.2.2 *SECONDARY ENDPOINTS*

The following secondary endpoints will be derived:

- Attack rate: a successful attack is defined as having at least two positive swabs (derived for both qPCR and culture) within the timespan of two consecutive days
- Time to start of viral shedding (hours) = (datetime of first of two positive swabs within 2 consecutive days - challenge datetime)/(60*60)
 - Time will be rounded as detailed in section 5.3.4
 - All time points (including unscheduled time points) from day 2 to day 10 will be considered.
 - Subjects not having at least two positive swabs (within 2 consecutive days) will be censored on the last viral load assessment
 - This endpoint will be derived for both qPCR and culture
- Peak viral shedding = highest viral load concentration
 - All time points (including unscheduled time points) from day 2 to day 10 will be considered.
 - Subjects not having at least two positive swabs (within 2 consecutive days) will be excluded from this analysis (peak viral shedding not calculated).
 - This endpoint will be derived for both qPCR and culture

	Statistical Analysis Plan	
FLU010	Final analysis	Final 3.0 of 15JUN2020

- Time to peak of viral shedding (hours) = (datetime of highest viral load concentration - challenge datetime)/(60*60)
 - Time will be rounded as detailed in section 5.3.4
 - All time points (including unscheduled time points) from day 2 to day 10 will be considered.
 - In case of identical peak values, the first in time will be considered.
 - Subjects not having at least two positive swabs (within 2 consecutive days) will be censored on the last viral load assessment
 - This endpoint will be derived for both qPCR and culture
- Time to cessation of viral shedding (hours) = (datetime of first negative swab following the last positive swab - challenge datetime)/(60*60)
 - Time will be rounded as detailed in section 5.3.4
 - All time points (including unscheduled time points) from day 2 to day 10 will be considered.
 - Subjects not having at least two positive swabs (within 2 consecutive days) will be excluded from this analysis (time to cessation not calculated).
 - An event is defined as having two consecutive negative swabs not followed by a positive swab. Subjects without an event will be censored on the last viral load assessment.
 - This endpoint will be derived for both qPCR and culture

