- Duration of viral shedding (hours) = (datetime of first negative swab following the last positive swab - datetime of first positive of two positive swabs within 2 consecutive days)/(60*60)
 - Duration will be rounded as detailed in section 5.3.4
 - All time points (including unscheduled time points) from day 2 to day 10 will be considered.
 - Subjects not having at least two positive swabs (within 2 consecutive days) will be excluded from this analysis (duration of viral shedding not calculated).
 - The end of viral shedding is defined as two consecutive negative swabs not followed by a positive swab. If this does not occur, the end of viral shedding will be set to the last viral load assessment.
 - This endpoint will be derived for both qPCR and culture
- vAUC based on culture values will be derived following the same rules as for the primary endpoint

	Statistical Analysis Plan	
FLU010	Final analysis	Final 3.0 of 15JUN2020

- Rate of virologically confirmed ILI: virologically confirmed ILI is defined as having a positive swab and a respiratory or flu-like symptom occurring on two consecutive days
 - A positive swab is defined as a positive qPCR.
 - All time points (including unscheduled time points) from day 2 to day 10 will be considered.
 - Positive swab and flu-like symptom have to occur on the same two consecutive days.
 - Respiratory or flu-like symptom can be any of the following signs or symptoms collected on the SSC: runny nose, sneezing frequency, sinus pressure/pain or facial pain, sore throat, difficulty swallowing, teary/watery eyes, painful eyes, aversion to light, dry cough, productive (wet) cough, difficulty breathing/tight chest, feverish, chills or shivering, sweating, lymphadenopathy
- Overall SSC AUC
 - AUC will be derived following the same rules as for the primary endpoint and rounded as detailed in section 5.3.4
 - SSC AUC will be calculated using the overall SSC score
 - Overall SSC score = arithmetic mean of all items
 - As lymphadenopathy is assessed only once a day, the value collected for that day will be used for both the AM and PM assessments in the calculation of SSC score.
 - Missing items will be handled as detailed in section 5.3.1

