- Duration of symptoms (hours) = (datetime of first zero overall SSC score following the last non-zero overall SSC score - datetime of first of two non-zero overall SSC scores within 2 consecutive days)/(60*60)
 - Pre-challenge time points will not be considered.
 - Duration will be rounded as detailed in section 5.3.4
 - Subjects not having at least two non-zero overall SSC scores (within 2 consecutive days) will be excluded from this analysis (duration not calculated).
 - The end of symptoms is defined as two timepoints with zero overall SSC score not followed by a timepoint with non-zero overall SSC score. If this does not occur, the end of symptoms will be set to the last evaluable SSC assessment.

	Statistical Analysis Plan	
FLU010	Final analysis	Final 3.0 of 15JUN2020

- Total days of fever = total number of days on which body temperature > 38°C
 - All time points (including unscheduled time points) from day 1 to day 11 will be considered, except for pre-challenge time points.
- Total mucus production (g) = (summed weight of all used bags + all used tissues + all returned clean tissues) - (summed weight of clean bags containing clean tissues)
 - Total mucus production will not be calculated for challenge cohorts 1 to 4 (due to problems with data collection for these cohorts).
 - Total mucus production will only be calculated in case all tissues were returned (sum of clean and used tissues returned should be 20 tissues for each bag).
 - Negative results for total mucus production within 2 SE of the mean result (within treatment group), will be set to zero.
- Local SSC score = arithmetic mean of local symptom items
Missing items will be handled as detailed in section 5.3.1
- General SSC score = arithmetic mean of general symptom items
Missing items will be handled as detailed in section 5.3.1

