2.1.3 Inferential statistics

All statistical comparisons will be made using two-sided tests at the 0.05 significance level unless specifically stated otherwise. As this is a proof-of-concept study, no correction method for multiple testing is foreseen. P-values should thus be interpreted accordingly.

Difference between MVA-NP+M1 and placebo in AUC (qPCR vAUC - primary analysis, culture vAUC, overall, local and general SSC AUC) and peak viral shedding/symptoms will be analysed using a Mann-Whitney U test. Additionally, adjusted difference between MVA-NP+M1 and placebo in AUC (qPCR vAUC, culture vAUC and overall SSC AUC) will be analysed using an ANCOVA model with treatment, sex, time since vaccination (see section 4.6.2) and challenge cohort as covariates.

Difference between MVA-NP+M1 and placebo in attack rate and virologically confirmed ILI will be analysed using a Fisher exact test.

Time to parameters will be analysed using Kaplan-Meier time to event analysis, with a log-rank test to compare MVA-NP+M1 and placebo.

Difference between MVA-NP+M1 and placebo in total days of fever will be tested using a zero inflated Poisson model.

Difference between MVA-NP+M1 and placebo in total mucus production will be tested with a t-test. Normality will be tested using a Shapiro-Wilk test. In case normality or homogeneity of variances assumption are not valid, a Mann-Whitney U test will be used.

Difference between MVA-NP+M1 and placebo in overall SSC changes from baseline will be analysed using a mixed model for repeated measurements (MMRM). The

	Statistical Analysis Plan	
FLU010	Final analysis	Final 3.0 of 15JUN2020

model will include treatment, sex, challenge cohort, timepoint and treatment by timepoint interaction terms as fixed effects, with baseline value and time since vaccination (see section 4.6.2) as covariates. Within-subject correlation will be modeled by assuming an unstructured (UN) covariance matrix for the error terms. If the model does not converge upon using UN, the following covariance structures will be tested for convergence (in order): heterogeneous Toeplitz (TOEPH), heterogeneous autoregressive first order (ARH(1)), heterogeneous compound symmetry (CSH), Toeplitz (TOEP), autoregressive first order (AR(1)) and compound symmetry (CS).

A similar MMRM model will be used for viral load (qPCR and culture) actual values, without the baseline covariate.

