2.1.4 Presentation of results

2.1.4.1 QPCR VIRAL SHEDDING

qPCR vAUC table will show descriptive statistics and the p-value of the Mann-Whitney U test for comparison of MVA-NP+M1 and placebo (primary analysis). Additionally, a table will report the results of the ANCOVA model, including the least square means per treatment group with 95% CI, least square mean differences (MVA-NP+M1 - placebo) with 95% CI and 2-sided p-value for testing differences between treatment groups.

Log qPCR and culture values and SSC scores will be summarised by means of descriptive statistics at each timepoint. Actual values and changes will be tabulated separately. The adjusted means by treatment group at each timepoint from the MMRM will be tabulated and presented graphically.

A frequency tabulation will show the number and percentage of successful attacks, with exact 95% CI and will also report the Fisher exact p-value for comparison of MVA-NP+M1 and placebo (secondary analysis). A similar table will also be created for virologically confirmed ILI.

For time to start/peak/cessation of viral shedding/feel well enough to go to work, the following results will be reported: number and percentage of events, number and percentage of censored observations, Q1, median and Q3 time with 95% CI and p-value (MVA-NP+M1 vs. placebo) using log-rank test.

Duration of viral shedding and peak viral shedding tables will show descriptive statistics and for peak viral shedding also the p-value of the Mann-Whitney U test for comparison of MVA-NP+M1 and placebo.

A listing will be prepared showing all derived parameters and the log qPCR values.

	Statistical Analysis Plan	
FLU010	Final analysis	Final 3.0 of 15JUN2020

Mean (SE) log qPCR and culture values and SSC overall score over time will be plotted. For all three time to parameters, Kaplan-Meier plots will be prepared.

A list of tables, figures and listings can be found in section 8

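### Peak, cessation and duration of shedding and symptoms are analysed only in infected or symptomatic participants under an ITT label, and unfinished durations are counted as complete, contrary to the protocol

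*SAP*

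**What the plan says.** **Who is analysed.** For peak viral shedding, SAP 2.1.2.2 states: "Subjects not having at least two positive swabs (within 2 consecutive days) will be excluded from this analysis (peak viral shedding not calculated". Time to cessation and duration of shedding carry the same exclusion, for both qPCR and culture. SAP 2.1.2.3 excludes participants without two non-zero overall SSC scores within two consecutive days from peak, cessation and duration of symptoms. The nine resulting tables (14.2.1.5, .7, .8; 14.2.2.4, .6, .7; 14.2.3.5, .7, .8) are listed as ITT, which SAP 5.1.1 defines as everyone randomised and inoculated. Time to start and time to peak, by contrast, keep everyone and censor those without an event.

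**What is tested.** Under SAP 2.1.3, peak is compared by Mann-Whitney and the time-to endpoints, including cessation, by log-rank. Duration is not tested: "Duration of viral shedding and peak viral shedding tables will show descriptive statistics", with a p-value added for peak only. SAP 2.1.4.3 treats symptoms in the same way.

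**Unfinished episodes.** For duration of shedding: "If this does not occur, the end of viral shedding will be set to the last viral load assessment". For duration of symptoms: "If this does not occur, the end of symptoms will be set to the last evaluable SSC assessment". For time to cessation, the same participants are censored.

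**The protocol.** Section 9.1.2.2 says that "duration of viral shedding will be summarized by the Kaplan-Meier method", with a log-rank test. Section 9.1.2.3 says the same for symptom duration. SAP 6.1, on changes not covered by amendment, reads NAP.

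**The concern.** Becoming infected or symptomatic after challenge happens after randomisation and is something the vaccine is meant to influence. Restricting a comparison to those who became infected drops more people from the arm where the vaccine prevented infection, and those left need not be alike. A reader who sees an ITT label and a p-value would take it as a randomised comparison. Such a result could show nothing while the vaccine prevents infection, or appear to favour placebo if the prevented infections were the mild ones.

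The duration rule is a separate matter. If the vaccine shortens shedding, more placebo recipients are still positive at the last swab. Ending their episodes there shortens the longer arm more and understates the difference.

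**Working it through.** **Inputs from the documents.** Numbers challenged: "A total of 80 participants from the MVA-NP+M1 group and 54 from the saline Placebo group are challenged" (SAP 1.2). Infection: "with a 83% attack rate and 30% efficacy, approximately 20 of the 80 vaccinated participants will have a zero AUC" (protocol synopsis). Tests: "two-sided tests at the 0.05 significance level" (SAP 2.1.3). The documents give no mean or SD for peak or duration, so every distribution below is an assumption.

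**1. The plan's own figure.** 80 × 0.83 × 0.30 = 19.9, which reproduces the 20. That product counts infections prevented. Another 80 × 0.17 = 13.6 vaccinees would be uninfected anyway.

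**2. Who would be excluded from the qPCR tables.**
- Vaccine: 80 × (1 − 0.83 × 0.70) = 33.5, or 42%.
- Placebo: 54 × 0.17 = 9.2, or 17%.
- Left in the analysis: 80 × 0.581 = 46.5 against 54 × 0.83 = 44.8.

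This takes the 83% to apply to the two-positives rule. The documents give no corresponding figure for culture or symptoms.

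**3. Peak viral load.** Simulation with 80:54 challenged, 83% placebo infection and 30% of infections prevented. Peak in the infected is assumed Normal(6, SD 1.5) log10, floored at 1, with 3,000 trials per row. Selection is the correlation between the peak a participant would have had and the score that decides prevention: 0 means prevention at random, 1 means the mildest are prevented. In the all-ITT column the uninfected score 0.

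| Selection | Further log10 reduction in the infected | Restricted: significant for vaccine | Restricted: significant the wrong way | All ITT: significant for vaccine |
|---|---|---|---|---|
| 0 | 0 | 3% | 2% | 70% |
| 0.5 | 0 | 0.1% | 22% | 44% |
| 1 | 0 | 0% | 70% | 17% |
| 0 | 0.5 | 31% | 0.1% | 93% |
| 0.5 | 0.5 | 7% | 1% | 79% |
| 1 | 0.5 | 0.4% | 10% | 56% |

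With no effect in the infected, the restricted mean difference (vaccine minus placebo) is 0.0, +0.37 and +0.75 log10 for selection 0, 0.5 and 1.

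**4. Time to cessation.** Assumed shedding start 1 to 3.5 days after challenge, lognormal duration (median 5 days, log SD 0.5), last swab at 9.5 days, 1,500 trials per case. With no effect in the infected, the restricted log-rank is significant for vaccine in 3%, 0.1% and 0% of trials, and the wrong way in 3%, 16% and 47% (selection 0, 0.5, 1). If the vaccine also shortens infected episodes by 15%, the wrong-way rates fall to 0.1%, 0.6% and 5%.

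**5. Duration with unfinished episodes ended at the last swab.** The last swab is on the evening of Day 10: 9 × 24 + 12 = 228 h after challenge. Assumed start Normal(48, 12) h; gamma durations with placebo SD 60 h; vaccine mean 20% or 30% shorter, with its SD scaled in proportion.

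| Placebo mean (h) | Shortening | True difference (h) | Difference shown (h) | Ratio |
|---|---|---|---|---|
| 140 | 20% | 28.0 | 20.4 | 73% |
| 140 | 30% | 42.0 | 32.5 | 77% |
| 160 | 20% | 32.0 | 20.6 | 64% |
| 160 | 30% | 48.0 | 33.7 | 70% |
| 180 | 20% | 36.0 | 19.5 | 54% |
| 180 | 30% | 54.0 | 33.0 | 61% |

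With SD 60 h in both arms the ratio is about 65% to 86%. Lognormal durations (log SD 0.5, 30% shorter, start 1 to 3.5 days) with placebo medians of 4, 6 and 8 days give 1.14/1.36 = 84%, 1.18/2.04 = 58% and 0.98/2.72 = 36%. The last is an extreme case, in which 58% of placebo episodes are unfinished. The sign never changed.

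**The case against.** **Prevention is measured elsewhere in all challenged participants.** This stands. Primary vAUC, attack rate, ILI, SSC AUC and the viral-load MMRM have no such exclusion. For 83% against 58.1% infected, the attack-rate comparison has about 88% power. The affected endpoints are secondary or exploratory, and SAP 2.1.3 describes a proof-of-concept study without multiplicity control.

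**The restricted test is sometimes the better one.** This also stands. The stated hypothesis is reduced replication and symptoms, not only prevention. With no prevention, peak Normal(6, SD 1.2), and a 0.5, 0.8 or 1.0 log10 reduction in the infected, the restricted test has 54%, 92% and 98% power against 37%, 70% and 85% for all ITT. There the restricted test is unbiased and stronger. Under strong selection with no effect in the infected, all-ITT power is low too (17% for peak).

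**The rule is open and prespecified.** True, and the tables report the number analysed. The protocol makes ITT the default efficacy set but names no population for peak and leaves detail to the SAP. The silence in SAP 6.1 is therefore a clear omission only for duration.

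None of this turns the peak and cessation p-values into randomised comparisons, justifies the ITT label, or explains why a participant still shedding is censored for cessation but counted as finished for duration.

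**Conclusion.** The point holds as a should-fix. The restriction depends on a post-randomisation outcome and, on the protocol's own inputs, would remove 42% of vaccinees and 17% of placebo recipients from the qPCR tables. The peak and cessation p-values can miss a prevention effect: for peak, 3% against 70% when prevention is at random and the infected are unaffected. Wrong-way results need preferential prevention of mild infections, an assumption the documents neither support nor exclude. They become much rarer once the vaccine also lowers load or shortens shedding in the infected.

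The duration rule shrinks the difference to roughly 54–86% of the truth under the gamma durations assumed, and further if most placebo episodes outlast the swabs. It departs from the protocol without being declared.

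A reader might infer three stronger things that the documents do not support:
- That the duration rule can reverse the effect. It only attenuates, and no p-value is attached.
- That unfinished episodes are mishandled throughout. Cessation is correctly censored within its subset.
- That the trial's main conclusion is at risk. The primary endpoint keeps everyone.

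**What to change.** 1. **Duration of shedding and of symptoms:** censor at the last swab or SSC those without two consecutive negative or zero assessments, and restore the Kaplan-Meier and log-rank analysis of protocol 9.1.2.2 and 9.1.2.3.
2. **Peak viral load and peak symptoms:** add a Mann-Whitney analysis in all ITT participants using the actual highest value. SAP 5.3.3 already sets not-detected viral load to log10 0, so no new imputation rule is needed.
3. **Restricted peak, cessation and duration tables:** keep them, label them as conditional on infection or symptoms instead of ITT, and state that their p-values are not randomised comparisons.

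An all-ITT cessation analysis that scores the never-infected as 0 is optional. It is a composite, because someone who never shed has no natural cessation time.

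The cost is SAP wording and reprogramming of the nine tables, with no new data. The downside is that all-ITT peak loses power if the vaccine only lowers load without preventing infection, which is why both versions should be shown.
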